1.4 Known and Potential Risks and Benefits of AR101

1.4.1 Risks

Peanut is a commonly consumed food and as such has a well-understood safety profile. Except for allergic reactions in subjects with peanut allergy, it does not cause discernible side effects in humans.

In subjects with peanut allergy, there have been many OIT studies performed using procedures and dosing similar to those proposed in this study. In general, the safety profile has been very good across the studies, and based on those studies, approximately 80%, 15%, and <1 % of the subjects are expected to have mild, moderate, or severe symptoms, respectively, during some point in their dosing with the peanut OIT. It is important to note that essentially all AEs have been allergy related, predictable, and reversible. The major atypical AE from peanut OIT that has been reported in the literature is eosinophilic

esophagitis (EoE), affecting an estimated 3 to 4% of OIT recipients (Lucendo et al, 2014), which is thought to be reversible upon stopping dosing.

The buildup and daily maintenance doses of peanut OIT may cause allergic symptoms including sneezing, rhinorrhea, urticaria, angioedema, flushing, flares of eczema, ocular, nasal, oral and/or throat pruritus, nausea, vomiting, abdominal discomfort, cough, wheezing, and/or shortness of breath in addition to severe anaphylaxis. The likelihood of a subject experiencing a severe allergic symptom is expected to be lessened by initiating dosing at extremely small amounts of AR101 and by buildup of dosing under observation in a clinical setting until the maintenance dose is achieved.

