Based on experience from Phase 2, most acute allergic responses to dosing that are characterized by mild symptoms would be anticipated to meet the above criteria. If, however, an allergic response to dosing is characterized by mild symptoms that do not meet all of the above criteria (eg, has mild symptoms occurring in 2 or more organ systems, requires treatment with 2 doses of antihistamine or 1 dose epinephrine, shows progression in severity or distribution over time, is protracted in duration, or includes objective wheezing), then even though the allergic symptoms may be mild, the dose should be assessed to be not tolerated. If a dose elicits mild symptoms that do not fit all of the above criteria and the dose is assessed to be tolerated, then a brief explanation as to why the dose was considered tolerated must be recorded in the CRF.

Moderate symptoms: In general, if a dose elicits moderate symptoms, the dose will be assessed as not tolerated. There may, however, be rare occasions when a dose eliciting moderate symptoms could be assessed as tolerated. Generally, this would only be the case for a transient, self-limited (requiring no intervention and resolving completely) symptom occurring in a single organ system. In addition, typically the symptom would be subjective only. Any dose associated with moderate symptoms and assessed as tolerated must be accompanied by a brief explanation in the CRF as to why the dose was considered tolerated.

Severe symptoms: If a dose elicits severe symptoms, the dose will be assessed as not tolerated. Whenever a dose elicits an allergic response characterized by 1 or more severe symptoms, the crucial decision, after adequate treatment for the allergic reaction has been administered, will be to determine whether the subject should continue in the study, dosing at a reduced dose level, or be discontinued early from the study. Please refer to individual stopping rules in [Section 7.8.2](#).

The determination of tolerability will decide the course of action to be taken in response to dose-related reactions ([Section 6.5.3](#)).

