- Moderate symptoms occurring with a new dose level would indicate lack of tolerability, with rare exceptions. Exceptions would generally be for a transient, self-limited (requiring no intervention and resolving completely) symptom of moderate intensity occurring in a single organ system. In addition, the symptom would typically be subjective. Any dose associated with moderate symptoms and assessed as tolerated must be accompanied by a brief explanation in the CRF as to why the dose was considered tolerated; (see [Section 6.5.2](#), for moderate symptoms assessed as tolerated). If moderate symptoms occur with the first dose at a new dose level, except for rare instances described above, the dose will be *assessed as not tolerated*. The action taken should be to have the subject return to the CRC the next day for dosing at the last tolerated dose under medical supervision. If this reduced dose elicits no allergic symptoms (ie, is well tolerated), the subject will continue that daily home dose level for an additional 2 weeks.

If the subject experiences mild symptoms at the reduced dose, the procedures for responding to a dose with mild symptoms should be followed (see above). If the subject experiences moderate symptoms at the reduced dose level, the subject should return to the CRC the next day and receive a further 1- or 2-step dose reduction (per investigator judgment). If this reduced dose is well tolerated, it will be continued as the daily home dose for ≥ 2 weeks before re-escalation is attempted in the CRC. If the dose is not well tolerated, but elicits mild symptoms, then the treatment procedures for responding to mild symptoms should be followed (see above). If, however, the subject again experiences moderate symptoms at the reduced dose level, a discussion with the Medical Monitor is to ensue to reach a decision as to whether to continue the subject in the study.

In the rare instance that a dose eliciting moderate symptoms is *assessed as tolerated*, then the actions taken should be the same as for a dose with mild symptoms *assessed as tolerated*.

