Table 6: Treatment(s) for Reactions during the Up-dosing Period by Severity of Reaction

Reaction Severity ^a	Treatment(s)
Mild acute allergic reactions requiring treatment	Antihistamines
Moderate acute symptoms requiring treatment	Antihistamines and/or epinephrine, as indicated
Severe symptoms	Antihistamines and/or epinephrine, as indicated

Assessment of severity of reaction is described in [Section 6.5.1](#). Assessment of tolerability of an individual dose is described in [Section 6.5.2](#).

- Treatment of acute reactions should be with either an antihistamine and/or epinephrine, along with IV fluids, a beta-agonist (eg, albuterol, by inhaler or nebulizer), oxygen, and/or glucocorticosteroids, as indicated. Many mild acute allergic reactions can be transient and self-limiting, requiring no therapeutic intervention. Others, however, may require treatment. Generally, for mild symptoms requiring treatment, the subject should receive antihistamines.
- Acute allergic reactions manifesting with moderate symptoms will generally require therapeutic intervention, although some, even moderate, symptoms may on rare occasion be so transient as to require no specific treatment. Generally, for moderate symptoms requiring treatment, the subjects should receive antihistamines and/or epinephrine, as indicated. If there is uncertainty as to the severity of the reaction, administering epinephrine would be considered the most appropriate course of action.
- Generally, severe symptoms will require treatment with epinephrine at a minimum. If severe symptoms that qualify as stage 3 anaphylaxis (as defined in [Appendix 3](#)) occur at any time, dosing with study product will stop and the subject will be discontinued from the study as an escalation failure nonresponder.

The procedures(s) that should be implemented after treatment of a reaction experienced during the Up-dosing period are summarized in [Table 7](#). An explanation follows the table.

Table 7: Procedure(s) Following Treatment of a Reaction Experienced during the Up-dosing Period

Treatment Given for Reaction	Procedure(s) Following Treatment
Antihistamines only	
 Continue dose escalation
Epinephrine: ≥ 2 doses taken either in CRC or at home	
 Discontinue dosing Subject returns to CRC 14 days after last dose for Early Discontinuation Visit

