Epinephrine: single dose given in CRC	
 Stop dosing at CRC Reduce next dose by 2 doses, both to be administered at CRC Continue bi-weekly escalation
Epinephrine required for a second consecutive time during, or after, 1 escalation attempt	
 Dose reduced by 2 dose levels. Reduced dose level continued for 6 to 8 weeks Escalation may be attempted after 6 to 8 weeks
Epinephrine required for a third consecutive time during an escalation attempt	
 Discontinue dosing Subject returns to CRC 14 days after last dose for Early Discontinuation Visit
Epinephrine: single dose at home	
 Not counted in the total count of epinephrine uses unless severe anaphylaxis has occurred Subject returns to CRC for an observed dose under medical supervision prior to resuming any dosing at home

CRC = clinical research center.

- Antihistamines
If a subject receives antihistamines only, the dose escalation can be continued. If epinephrine is administered, then a different course of action is to be taken (see below).
- Epinephrine – General Procedures
Any reaction to study product (in clinic or at home) that requires more than 2 doses of epinephrine will halt all further dosing of study product for the individual. The subject will be asked to return to the CRC 14 days following the last dose of study product to undergo an Early Discontinuation Visit ([Section 6.3.10](#)).
- Epinephrine – Single Dose Administered at Clinic
If a single administration of epinephrine is required during or after a dose-escalation in the clinic, no further dosing of study product is to occur at that visit. The next dose of study product is to be reduced by 2 dose levels and administered in the CRC, but biweekly dose escalation should continue.
If a single administration of epinephrine is required for a second consecutive time during, or after, 1 escalation attempt, the dose should be reduced by 2 dose levels, and the subject continued at that dose level for 6 to 8 weeks. After 6 to 8 weeks at the reduced dose, an escalation attempt may be tried in clinic.

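### Table 7 lets dose escalation continue after any Up-dosing reaction treated with antihistamines only, without the severity and tolerability conditions that Sections 6.5.2, 6.5.5 and 6.5.5.1.1 attach to the same reaction

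*Protocol*

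**What the plan says.** Two sets of instructions in the Protocol apply to a reaction during Up-dosing.

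**Keyed to treatment (Section 6.5.6).** Table 7 lists what follows each kind of treatment. Its antihistamines-only row reads "Continue dose escalation", and the explanatory text adds "If a subject receives antihistamines only, the dose escalation can be continued". Neither is limited to mild reactions or to doses judged tolerated. The text after Table 6 says: "Generally, for moderate symptoms requiring treatment, the subjects should receive antihistamines and/or epinephrine, as indicated". Antihistamines alone are therefore an allowed treatment for a moderate reaction.

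**Keyed to severity and tolerability (Sections 6.5.2, 6.5.5 and 6.5.5.1.1).** Section 6.5.5.1.1 begins its rule "If moderate symptoms occur with the first dose at a new dose level, except for rare instances described above, the dose will be" and completes it by classing that dose as not tolerated. On the next step it says: "The action taken should be to have the subject return to the CRC the next day for dosing at the last tolerated dose". If the lower dose causes no symptoms, the subject stays on it for 2 more weeks. Section 6.5.5 makes a reduction of 1 or 2 levels the default for any dose not tolerated. Section 6.5.2 also lists a mild reaction that "requires treatment with 2 doses of antihistamine or 1 dose epinephrine" among those that should be assessed as not tolerated, subject to investigator judgment and a recorded explanation if the investigator decides otherwise.

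Two sentences bear on which set governs. Section 6.5.2 closes by saying that the tolerability determination decides the response to a dose-related reaction. Section 6.3.3.1 refers dose reductions to Section 6.5.5 and ties their size to symptom severity.

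**The concern.** A moderate reaction to a new dose level that is treated with an antihistamine falls under both sets. A site working from Table 7 sees that escalation goes on. A site working from Section 6.5.5.1.1 sees a step-down the next day. Table 7 also sets dose reductions and discontinuation for the epinephrine rows, so it reads as a complete dosing rule rather than a list of drug treatments, and nothing in its antihistamine row sends the reader elsewhere.

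The first thing at stake is the dose a subject takes after a reaction. Several reported results also depend on that step:

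- the frequency of treatment-related AEs, which is the primary endpoint and is summarized for Group 1 over initial escalation and Up-dosing (SAP 6.1 and 10.3);
- the Kaplan-Meier time to 300 mg (SAP 10.1);
- escalation-failure status, through the 40-week limit (Protocol 3.1.2) and the limit of three consecutive failed attempts (6.3.3.1).

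The analyses are descriptive, so no test is invalidated. The risk is that these summaries mix two ways of handling the same reaction, with site practice deciding which.

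**Working it through.** **1. The passages side by side**

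| Reaction, treated with antihistamines only | Table 7 and its text | 6.5.2, 6.5.5, 6.5.5.1.1 |
|---|---|---|
| Mild, judged tolerated | Escalation continues | Dose repeated the next day; level generally kept, with discretion to step back if mild symptoms recur |
| Mild, judged not tolerated (for example, 2 antihistamine doses) | Escalation continues | One-step reduction the next day, then 2 weeks if tolerated |
| Moderate, first dose at a new level | Escalation continues | Not tolerated; last tolerated level the next day, then 2 more weeks if symptom-free |

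The first row is broadly compatible. The second and third are not, on the face of Table 7. The exception in 6.5.5.1.1 for moderate symptoms does not close the gap, because it is generally reserved for symptoms that needed no intervention.

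Table 6 also lists antihistamines and/or epinephrine for severe symptoms, but the text below it says these generally need epinephrine at a minimum. I therefore put little weight on the severe case.

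**2. What differs for one episode**

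Take a moderate reaction at the visit in week *t*, at level *k*. If escalation simply continues, level *k*+1 is due at *t* + 2. If the subject steps down, tolerates the lower level and succeeds on the first retry, level *k* is retried at *t* + 2 and level *k*+1 is due at *t* + 4. The difference is (t + 4) − (t + 2) = 2 weeks per episode. It is longer if the step-down or the retry fails.

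**3. How many subjects**

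Inputs:
- Planned Group 1 size: 130 (Protocol 7.8.3).
- Share with moderate symptoms: 15%. Protocol 1.4.1 says "approximately 80%, 15%, and <1 % of the subjects are expected to have mild, moderate, or severe symptoms" at some point during peanut OIT dosing. This is an expectation from earlier studies with no inputs shown, so it cannot be recomputed.
- *f*, the fraction of those subjects who have a qualifying reaction treated with antihistamines only: not given in the documents. I assume 10% to 100%.

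Formula: affected subjects = 130 × 0.15 × *f*.

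| *f* | Share of Group 1 | Subjects of 130 |
|---|---|---|
| 100% (ceiling) | 15% | 19.5 |
| 75% | 11.3% | 14.6 |
| 50% | 7.5% | 9.8 |
| 25% | 3.8% | 4.9 |
| 10% | 1.5% | 2.0 |

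The 130 is described as 25% of ARC003 enrollment allowing for 5% dropout. With 500 enrolled, 125/0.95 = 131.6 is close to it; 125 × 0.95 = 118.75 is not. At 119 subjects the ceiling would be 119 × 0.15 = 17.9, which changes little.

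**4. Reach beyond the first dose at a new level**

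Section 6.5.5.2 sends home doses judged not tolerated to Section 6.5.5. Section 6.5.7 and Table 8 send QD Maintenance and QD Extended Maintenance, including Group 2, to the Up-dosing procedures. The same mismatch can arise there. I have not tried to count these cases, or mild reactions judged not tolerated.

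**The case against.** The strongest reply is that the protocol already settles the matter. Section 6.5.2 says tolerability decides what follows, 6.3.3.1 ties dose adjustment to severity, and 6.5.5 makes reduction the default for a dose not tolerated. Section 6.5.5 is the one titled as dose adjustment, whereas 6.5.6 is titled as pharmacological and supportive treatment, and the note under Table 6 points back to 6.5.1 and 6.5.2. On this view Table 7 only adds consequences for epinephrine use. Much of this stands: a reader might infer that the protocol never says which rule prevails, and that would be wrong. But the guidance is general and sits elsewhere. Table 7 and its text do not invoke it when stating the next dosing step.

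A reader might also infer that the two instructions are flat opposites. The documents do not support that either. The 6.5.6 sentence is permissive. In the same table, the row for a single epinephrine dose in clinic combines a two-level reduction with continued biweekly escalation, so continuing can mean only that the schedule is not halted. The weakness of this reading is that the epinephrine row states its reduction and the antihistamine row states none. The text then says that epinephrine calls for a different course of action, which suggests that antihistamines alone call for no step-down.

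Finally, a reader might infer that about 15% of Group 1 would meet the conflict. The 15% covers moderate symptoms at any point in dosing, including those treated with epinephrine, those left untreated, and those occurring other than at a new level. It is a ceiling. A binomial interval around 19.5 would not help, because the main uncertainty is the unknown *f*.

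**Conclusion.** The mismatch is in the text and should be corrected, as a gap in reconciliation rather than an outright contradiction. For a moderate reaction to a new dose level treated with antihistamines only, Table 7 and its text read as a separate treatment-based rule that allows escalation to continue, while 6.5.5 and 6.5.5.1.1 step the dose down. The general statements in 6.5.2 and 6.3.3.1 favor a tolerability- and severity-based reading, but a site using Table 7 is not directed to them.

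The size is modest and uncertain: for moderate reactions, at most about 20 of 130 planned Group 1 subjects, and about 2 to 20 over the assumed range of *f*. This rests on the protocol's 15% applying to this population. Mild reactions judged not tolerated, and QD Maintenance and Extended Maintenance cases, would be additional and cannot be counted from the documents. Each episode shifts the up-dosing schedule by at least 2 weeks between the two readings, on the assumptions in the timing step.

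One caveat: Figure 3, the algorithm for poorly tolerated doses, is not reproduced in the text available to me and may contain a clarification. The point does not depend on the count. It matters because it concerns a safety-relevant dosing step and is cheap to settle. I take no view on which instruction is clinically right.

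**What to change.** Reconcile the antihistamines-only row of Table 7 and the text under it with Sections 6.5.2, 6.5.5 and 6.5.5.1.1, so that each combination of severity, tolerability assessment and treatment leads to one next step. Cross-reference the governing section in Table 7. Check that Table 6, Figure 3 and the referrals from 6.5.5.2 and 6.5.7 agree with the result. The sponsor's clinical team decides which instruction stands.

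The cost is a protocol clarification and a communication to sites. No visits, procedures or data collection are added.

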6.6 Missed Peanut OIT (Study Product) Doses during Up-dosing (Group 1)

Risk due to missed doses of study product is believed to be highest during the Up-dosing Period. The procedures to be followed after missed consecutive doses of study product during the Up-dosing Period is depicted in [Figure 5](#). Explanatory text follows the figure.

Figure 5: Procedures Following Missed Consecutive Doses of Peanut OIT

AE = adverse event; CRC = clinical research unit; OI = oral immunotherapy (ie, AR101 or study treatment).

- Miss 1-2 doses in a row – The next dose would be the current dose level and could be given at home
- Miss 3-4 doses in a row – The next dose would be the current dose and would be given under supervision in the CRC
- Miss 5-6 doses in a row – Initiate the next dose at approximately 50% of the last tolerated dose (to the nearest feasible available whole dose that is \leq 50% of the last tolerated dose). This dose is to be administered under supervision in the CRC. If tolerated, dose escalation may resume with dose increases of 1 dose level occurring no more frequently than weekly and generally no less frequently than every 4 weeks

until the subject has returned to the dose level at which the lapse in dosing occurred. If symptoms occur, the dosing guidelines for the up-dosing period apply.

- Missing ≥ 7 consecutive days of dosing due to non-compliance (ie, for any reason other than treatment of an AE or a study product dispensing error), constitutes an individual stopping rule and the subject is to stop taking study product. The subject will be considered an escalation failure nonresponder, and will be asked to return to the CRC 14 days following their last dose of study product to undergo an Early Discontinuation Visit ([Section 6.3.10](#)).
- Additionally, excessive missed dosing, defined as 3 consecutive days of missed doses on 3 occasions during the Up-dosing Period, for any reason other than treatment of an AE, constitutes an individual stopping rule and the subject is to stop taking study product. The subject will be considered an escalation failure nonresponder, and will be asked to return to the CRC 14 days following their last dose of study product to undergo an Early Discontinuation Visit ([Section 6.3.10](#)).
- If study product has been withheld for 8 to 14 consecutive days as treatment for an AE or due to a study product dispensing error, dosing may be reinitiated at approximately 25% of the last tolerated dose (to the nearest feasible available whole dose that is $\leq 25\%$ of the last tolerated dose) if the lapse in dosing occurred during the *Up-dosing Period*. If the lapse in dosing occurred during the *Maintenance Period*, (see [Figure 6](#)) dosing may, at the investigator's discretion, be reinitiated at 50% of the last tolerated dose (to the nearest feasible available whole dose that is $\leq 50\%$ of the last tolerated dose). The reduced dose is to be administered under supervision in the CRC. If tolerated, dose escalation may resume with dose increases of 1 dose level occurring no more frequently than weekly and no less frequently than every 4 weeks until the subject has returned to the dose level at which the lapse in dosing occurred. If symptoms occur, the dosing guidelines for the Up-dosing Period apply.

Figure 6: Procedures for Doses Withheld for 8 to 14 Days During the Maintenance Period

OIT = oral immunotherapy (ie, AR101, study product).

- If a subject on a QD dosing regimen has his/her study product withheld for ≥ 15 consecutive days for any reason, at any point in the study (with the exception of a dosing hiatus instituted for chronic/recurrent GI AEs at or before the 20 mg dose level, as per [Section 6.5.3.2](#)), the subject will be considered an escalation failure nonresponder, and will be asked to return to the CRC 14 days following their last dose of study product to undergo an Early Discontinuation Visit ([Section 6.3.10](#)).

During up-dosing, no attempt should be made to make up for a missed dose if greater than 6 hours have elapsed since usual time of dosing.

